7.15.1. Definition of Lesions

Tumor response will be assessed according to the RECIST (version 1.1; *Eisenhauer et al. 2009*). At baseline, tumor lesions/lymph nodes will be categorized measurable or non-measurable as follows:

Measurable disease

Measurable lesions are defined as those that can be accurately measured in at least one dimension (longest diameter to be recorded) as ≥ 20 mm (≥ 2 cm) by chest x-ray or as ≥ 10 mm (≥ 1 cm) with CT scan, MRI, or calipers by clinical exam (such measurements must be clearly documented). All tumor measurements must be recorded in millimeters (or decimal fractions of centimeters).

Malignant lymph nodes:

To be considered pathologically enlarged and measurable, a lymph node must be ≥ 15 mm in short axis when assessed by CT scan (CT scan slice thickness recommended to be no greater than 5 mm). At baseline and in follow-up, only the short axis will be measured and followed.

Non-measurable disease

All other lesions (or sites of disease), including small lesions (longest diameter < 10mm or pathological lymph nodes with ≥ 10 to < 15 mm short axis) as well as truly non-measurable lesions.

Bone lesions, leptomeningeal disease, ascites, pleural/pericardial effusions, lymphangitis cutis/pulmonitis, inflammatory breast disease, and abdominal masses (not followed by CT or MRI), are considered as non-measurable.

Special considerations regarding lesion measurability

Bone lesions, cystic lesions, and lesions previously treated with local therapy require particular comment:

Bone lesions:

- Bone scan, PET scan or plain films are not considered adequate imaging techniques to measure bone lesions. However, these techniques can be used to confirm the presence or disappearance of bone lesions.
- Lytic bone lesions or mixed lytic-blastic lesions, with identifiable soft tissue components, that can be evaluated by cross sectional imaging techniques such as CT or MRI can be considered as measurable lesions if the soft tissue component meets the definition of measurability described above.
- Blastic bone lesions are non-measurable.

Cystic lesions:

- Lesions that meet the criteria for radiographically defined simple cysts should not be considered as malignant lesions (neither measurable nor non-measurable) since they are, by definition, simple cysts.
- ‘Cystic lesions’ thought to represent cystic metastases can be considered as measurable lesions, if they meet the definition of measurability described above. However, if noncystic lesions are present in the same patient, these are preferred for selection as target lesions.

Lesions with prior local treatment:

- Tumor lesions situated in a previously irradiated area, or in an area subjected to other loco-regional therapy, are usually not considered measurable unless there has been demonstrated progression in the lesion. Study protocols should detail the conditions under which such lesions would be considered measurable.

7.15.2. Method of Assessment

The same method of assessment and the same technique have to be used to characterize each identified and reported lesion at screening, at end of treatment and during follow-up.

Clinically detected lesions will only be considered measurable when they are superficial (e.g., skin nodules and palpable lymph nodes).

Lesions on chest x-ray are acceptable as measurable lesions when they are clearly defined and surrounded by aerated lung. However, CT is preferable.

Conventional CT and MRI should be performed with contiguous cuts of 5 mm or less in slice thickness, if possible [minimum measurable lesion size: long axis \geq 10 mm (CT + MRI) and 2 x slice thickness, if the slice thickness is $>$ 5 mm].

Ultrasound may only be used as a possible alternative to clinical measurements for superficial palpable lymph nodes, subcutaneous lesions, and thyroid nodules.

7.15.3. Baseline documentation of 'target' and 'non-target' lesions

Only subjects with measurable disease at baseline should be enrolled in this study. For evaluation of tumor response, lesions present at screening will be separated into target and non-target lesions according to the following criteria:

Target Lesions:

- All measurable lesions up to a maximum of 2 lesions per organ and 5 lesions in total, representative of all involved organs, should be identified as target lesions and recorded and measured at baseline.
- Target lesions should be selected on the basis of their size (lesions with the longest diameter), be representative of all involved organs, but in addition should be those that lend themselves to reproducible repeated measurements. It may be the case that, on occasion, the largest lesion does not lend itself to reproducible measurement in which circumstance the next largest lesion which can be measured reproducibly should be selected.
- A sum of the diameters (longest for non- nodal lesions, short axis for nodal lesions) for all target lesions will be calculated and reported as the baseline sum diameters. This is the "sum of the longest diameters" (SLD). If lymph nodes are to be included in the sum, then only the short axis is added into the sum. The baseline sum diameters will be used as reference to further characterize any objective tumor regression in the measurable dimension of the disease.

Non-Target Lesions

- All other lesions (or sites of disease) including any measurable lesions over and above the 5 target lesions should be identified as non-target lesions and should also be recorded at baseline.

Measurements of these lesions are not required, but the presence, absence, or in rare cases unequivocal progression of each should be noted throughout follow-up.

- It is possible to record multiple non-target lesions involving the same organ as a single item on the eCRF (e.g. “multiple enlarged pelvic lymph nodes” or “multiple liver metastases”)

7.15.4. Evaluation of target lesions

- Measure LD (axial plane) for each target lesion
- Measure short axis for target lymph nodes
- Add these measurements to get the SLD
- If too small to measure, a default value of 5 mm is assigned. If the lesion disappears completely, the measurement is recorded as 0 mm.
- Splitting or coalescent lesions
 - If a target lesion fragments into multiple smaller lesions, the LDs of all fragmented portions are added to the sum
 - If target lesions coalesce, the LD of the resulting coalescent lesion is added to the sum

Table 7-3: Target Lesion Evaluation

Response	Definition
Complete Response (CR)	Disappearance of all target lesions. Any pathological lymph nodes (whether target or non-target) must have reduction in short axis to <10 mm.
Partial Response (PR)	At least a 30% decrease in the sum of diameters of target lesions, taking as reference the baseline sum diameters.
Progressive Disease (PD)	At least a 20% increase in the sum of diameters of target lesions, taking as reference the smallest sum on study (this includes the baseline sum if that is the smallest on study). In addition to the relative increase of 20%, the sum must also demonstrate an absolute increase of at least 5 mm. (Note: the appearance of one or more new lesions is also considered progression).

Response	Definition
Stable Disease (SD)	Neither sufficient shrinkage to qualify for PR nor sufficient increase to qualify for PD, taking as reference the smallest sum diameters while on study.

7.15.5. Evaluation of non-target lesions

Table 7-4: Non-Target Lesion Evaluation

Response	Definition
Complete Response (CR)	Disappearance of all non-target lesions and normalization of tumor marker level. All lymph nodes must be non-pathological in size (<10mm short axis).
Non-CR/Non-PD	Persistence of one or more non-target lesion(s) and/or maintenance of tumor marker level above the normal limits.
Progressive Disease (PD)	
Appearance of one or more new lesions and/or unequivocal progression of existing non-target lesions. Unequivocal progression should not normally trump target lesion status. It must be representative of overall disease status change, not a single lesion increase.
 
Although a clear progression of “non-target” lesions only is exceptional, the opinion of the treating physician should prevail in such circumstances, and the progression status should be confirmed at a later time by the review panel (or Principal Investigator).

7.15.6. Evaluation of Best Overall Response

The best overall response is the best response recorded from start of treatment until disease progression/recurrence (taking as reference for progressive disease the smallest measurements recorded since the start of treatment). The patient's best response assignment will depend on the achievement of both measurement and confirmation criteria. Responses will be assessed using CT scans or magnetic resonance imaging according to standard RECIST v1.1 criteria in order to assess disease progression. These criteria will also allow for patients who experience an initial disease

flare, and as some patients who will have a delayed response may experience an initial disease flare, these patients will be allowed to continue receiving study treatment beyond progression.

The following table provides overall responses for all possible combinations of tumor responses in target and non-target lesions with or without the appearance of new lesions:

Table 7-5: Time point response: subjects with target (\pm non-target) disease

Target lesions	Non-target lesions	New lesions	Overall response
CR	CR	No	CR
CR	Non-CR/non-PD	No	PR
CR	Not evaluated	No	PR
PR	Non-PD or not all evaluated	No	PR
SD	Non-PD or not all evaluated	No	SD
Not all evaluated	Non-PD	No	NE
PD	Any	Yes or No	PD
Any	PD	Yes or No	PD
Any	Any	Yes	PD

CR = complete response, PR = partial response, SD = stable disease, PD = progressive disease, and NE = inevaluable.

Note: To be assigned a status of PR or CR, changes in tumor measurements must be confirmed by repeat assessments that should be performed 6 weeks after the criteria for response are first met. In the case of SD, measurements must have met the SD criteria at least once after study entry at a minimum interval of 6 weeks.

7.15.7. Duration of Response

Duration of overall response: The duration of overall response is measured from the time measurement criteria are met for CR or PR (whichever is first recorded) until the first date that recurrent or progressive disease is objectively documented (taking as reference for progressive disease the smallest measurements recorded since the treatment started).

The duration of overall CR is measured from the time measurement criteria are first met category

when no lesions can be measured is not advised for CR until the first date that progressive disease is objectively documented.

Duration of stable disease: Stable disease is measured from the start of the treatment until the criteria for progression are met, taking as reference the smallest measurements recorded since the treatment started, including the baseline measurements.

7.16 SURVIVAL STATUS

Subjects will be followed up by clinic visits or phone call or another method of contact, for survival status every 3 months (± 1 month) for 2 years after treatment discontinuation or until death, whichever occurs first.

8 STATISTICAL ANALYSIS

This section presents general information about statistical considerations and concepts and a brief discussion on analysis methodology, as well as some data conventions. Detailed descriptions of the statistical analysis methods and data conventions that will be used in this study will be in a separate document; i.e., the Statistical Analysis Plan (SAP).

8.1 TREATMENT GROUPS

The following treatment groups will be assessed in the dose-finding portion of the study:

- 350 mg leronlimab (PRO 140) + AUC 5 Carboplatin
- 525 mg leronlimab (PRO 140) + AUC 5 Carboplatin
- 700 mg leronlimab (PRO 140) + AUC 5 Carboplatin

8.2 SAMPLE SIZE DETERMINATION AND RATIONALE

Up to 18 patients will be enrolled in the Phase Ib portion of the study. A total of 30 subjects will be enrolled in the Phase II portion.

8.3 RANDOMIZATION AND STRATIFICATION

Not applicable.

8.4 BLINDING

Not applicable.

8.5 INTERIM ANALYSIS

No interim analysis (IA) will be performed for efficacy. There will be a safety review, once all three (or six) subjects from each cohort complete the DLT evaluation period (defined as cycle 1 or the first 21 days of treatment).

The Sponsor's Medical Monitor, CRO Medical Monitor and study investigators must be satisfied with data obtained in Cohort A before allowing subsequent enrollment of Cohort B. Likewise, they must be satisfied with data obtained in Cohort B before allowing subsequent enrollment in Cohort C.

In addition, should any of the following events occur in any cohort during the DLT evaluation period, the Data Safety Monitoring Board (DSMB) will meet to review available study data and make a final decision for dose escalation to the next cohort:

- a. Death in any subject in which the cause of death is judged to be possibly, probably or definitely related to leronlimab (PRO 140)
- b. The occurrence in any subject of an anaphylactic reaction to leronlimab (PRO 140)
- c. The occurrence in any subject of a severe local injection site reaction (Grade 3 which is not resolved or recurs; or Grade 4) that precludes administration of consecutive leronlimab (PRO 140) doses.
- d. The occurrence in any subject of a life-threatening SAE whose causal relationship to leronlimab (PRO 140) is judged to be probable or definite
- e. The occurrence of one or more non-life-threatening SAEs whose causal relationship to leronlimab (PRO 140) is judged to be definite
- f. The occurrence, in one or more subjects, of Grade 4 laboratory abnormalities, judged to be probably or definitely related to receipt of leronlimab (PRO 140)
- g. The occurrence of hematologic and non-hematological adverse events, judged to be possibly, probably or definitely related to receipt of leronlimab (PRO 140) based on previous clinical experience and that are of CTCAE Grade 3 or greater severity. Permissible exceptions to this rule include Grade 3 fatigue of less than one week duration, and Grade 3 nausea, vomiting, and diarrhea that resolve within 48 hours following institution of appropriate supportive care.
- h. Hy's law
- i. Neutropenic fever
- j. Grade 4+ neutropenia or thrombocytopenia >7 days
- k. Grade 3+ thrombocytopenia with bleeding
- l. Grade 3+ electrolyte abnormality that lasts >72 hours, unless the patient has clinical symptoms, in which case all grade 3+ electrolyte abnormality regardless of duration should count as a DLT. Grade 3+ amylase or lipase elevation NOT associated with symptoms or clinical manifestations of pancreatitis does not need to be counted as a DLT
- m. For patients with hepatic metastases, AST or ALT >8xULN or AST or ALT >5x ULN for ≥ 14 days

8.6 GENERAL STATISTICAL CONSIDERATIONS

All collected study data will be presented in subject data listings. Statistical analyses will be performed using SAS® for Windows, version 9.3 or later. Descriptive statistics (n, mean, standard deviation, median, minimum and maximum) will be presented by treatment group for continuous

variables. Frequencies and percentages will be presented by treatment group for categorical variables.

8.6.1. Analysis Populations

8.6.1.1 Intent-to-Treat Population

The **Intent-to-Treat (ITT) population** is defined as the set of subjects who have received at least one dose of leronlimab (PRO 140) and have measurable disease at baseline. The ITT population will be used as the primary analysis population.

8.6.1.2 Per Protocol Population

The **Per Protocol (PP) population** is defined as the set of subjects who meet the ITT population requirements, were not associated with any major protocol violations and have received at least 2 cycles of treatment. This population will be identified before the database lock.

The PP analysis of primary and secondary endpoints will be considered supportive

8.6.1.3 Safety Population

The **Safety Population** will include all subjects who have received one dose of leronlimab (PRO 140). This population will be used for the analysis of safety parameters.

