4.3 TREATMENT PERIOD

Subjects who meet all eligibility criteria, as per data gathered from Screening Period are to be treated. All subjects who fail to meet eligibility criteria will be considered screen failure and exit the study without further evaluation

Phase Ib

The dose finding portion of study will follow a “3+3” design. The maximum sample size for this portion of the study is 18 subjects that will be followed by treatment according to the schedule described above starting on Cycle 1, Day 1.

Phase II

The maximum sample size for this portion of the study is 30 subjects that will be followed by treatment according to the schedule described above starting on Cycle 1, Day 1.

During the Phase Ib and Phase II of the study, treatment may continue until one of the following criteria applies:

- Disease progression,
- Intercurrent illness that prevents further administration of treatment,
- Unacceptable adverse event(s), or
- Withdrawal of consent

Each treatment cycle consists of 21 days. Leronlimab (PRO 140) will be administered subcutaneously weekly on Days 1, 8, and 15 in combination with carboplatin AUC 5 on Day 1 of each cycle (every 21 days). Day 1 of Cycle 2 begins at Day 22.

4.3.1. Treatment Cycle 1, Day 1

The following assessments will be performed at the first treatment visit of Cycle 1:

- Concomitant medications assessment (see [Section 7.5](#)),
- Vital Signs and body weight measurement (see [Section 7.6](#)),
- Physical examination, including evaluation of all body systems (see [Section 7.7](#))
- ECOG Performance Status (see [Section 7.8](#))

- 12-lead Electrocardiogram (see [Section 7.9](#))
- Collection of lab specimens (see [Section 7.11](#)) for
 - Complete blood count
 - Biochemistry
 - Urine pregnancy test, for female subjects of childbearing potential.
 - Urine sample for urinalysis parameters
 - CTCs PD-L1/CCR5 analysis
 - CTC and CAMLs analysis

Note: Complete blood count, biochemistry and urinalysis can be performed within 3 days prior to each cycle start.

- Leronlimab (PRO 140) Administration (see [Section 6.1.3](#))
- Carboplatin Administration (see [Section 6.2.5](#))
- Post Injection Site Evaluation (performed by Investigator) (see [Section 7.13](#))
- Toxicity assessment (see [Section 7.10](#)) and Review of Adverse Events (see [Section 9](#))

4.3.2. Treatment Cycle 1, Day 8 & Day 15

The following assessments will be performed at during the remaining visits (Day 8 and 15) in the first treatment cycle:

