6 STUDY TREATMENT

Eligible subjects will receive the combination leronlimab (PRO 140) and carboplatin. Leronlimab (PRO 140) will be administered weekly at a dose assigned at time of enrollment and carboplatin target of AUC 5 every 3 weeks as combination therapy until disease progression or intolerable toxicity.

Table 6-1: Treatment Administration Summary

Study Drug	Premedication	Dose	Route	Schedule	Cycle Length	Supportive Therapies
Leronlimab (PRO 140)	N/A	Assigned dose cohort*	SC	Start on Day 1 and every week thereafter	N/A	N/A
Carboplatin	Antiemetics	AUC 5	IV Infusion	Day 1 every 3 weeks (21 Days)	3 weeks (21 Days)	Omeprazole or similar agents, ondansetron or similar antiemetics

*Phase Ib: Cohort A: 350 mg PRO 140 SC weekly; Cohort B: 525 mg PRO 140 SC weekly; Cohort C: 700 mg PRO 140 SC weekly

*Phase II: MTD PRO 140 SC weekly

Supportive care: Any required supportive care treatment such as antibiotics, anti- emetics, proton pump inhibitors and others will be given per institutional standards.

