6.2.13. Carboplatin - Toxicity Management & Dose Delays/Modifications

The dose interruption, reduction, and permanent discontinuation for any toxicity are described below.

Dose interruption: Refer to table below. Recovery to acceptable levels must occur to allow carboplatin continuation.

Table 6-4: Carboplatin Dose Modification and Management

Toxicity	Grade/Description	Carboplatin
Hematologic Toxicities		
Thrombocytopenia	Grade 1	Maintain dose level.
	Grade 2	Hold dose & follow CBC weekly. Once \leq Grade 1 (platelets \geq 75,000/mm ³), resume at same dose.
	Grade 3	Dose reduction to AUC 4
	Grade 4	Permanently discontinue Carboplatin
Neutropenia	Grade 1 , 2 or 3 without fever	Maintain dose level.
	Grade 3 w/ fever or Grade 4	1st occurrence: Hold dose & follow CBC weekly. Once resolved to $> 1.0 \times 10^9/L$ (if neutropenia was the only toxicity noted), resume at same dose. If other toxicity was noted, resume with AUC 4. 2nd occurrence: Discontinue Carboplatin
Non-Hematologic Toxicities		
Allergic reaction or hypersensitivity	\leq Grade 3	Hold dose until resolved to \leq Grade 1 & then resume at same dose level.
	Grade 4	Permanently discontinue Carboplatin

Toxicity	Grade/Description	Carboplatin
Infection	Grade 1 or 2	Hold dose until systemic treatment for infection is complete. If no neutropenia, resume at same dose level. If neutropenic, follow instructions above (hematologic section). If no resolution after > 3 weeks: permanently discontinue Carboplatin
	Grade 3	Discontinue Carboplatin
Herpes zoster or simplex	Any grade	Hold dose until lesions are dry & then resume at same dose level.
Neuropathy	Grade 2 w/pain or Grade 3	Hold dose until resolved to \leq Grade 2 or baseline then resume at AUC 4. May continue on single-agent leronlimab (PRO 140) (per treating investigator's discretion)
	Grade 4	Permanently discontinue Carboplatin
Renal dysfunction	CrCl \leq 15 mL/min	Hold dose until CrCl $>$ 15 mL/min & then resume.

Note: Patients who discontinue carboplatin for any reason will be allowed to continue to receive leronlimab (PRO 140) per treating investigator's discretion. In such cases, patients will be re-consented so that they are appropriately informed of other treatment options that have demonstrated improvement in clinical outcomes.

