7.10 TOXICITY ASSESSMENT

Any subject who receives at least one dose of study therapy will be evaluable for toxicity endpoints. Each subject will be assessed for the development of toxicity according to the timeframe referenced in the Schedule of Events table. Toxicity will be assessed according to CTCAE v 5.0 criteria. Refer to [Section 3](#) for the assessment criteria for dose limiting toxicity under Phase Ib of the study. Also

refer to [Table 6-3](#) and [Table 6-4](#) for the dose modification and management of leronlimab (PRO 140) and carboplatin for any toxicity.

All subjects will be followed for adverse events for 30 days after last dose of leronlimab (PRO 140) and carboplatin, or until the subject starts a new treatment, whichever occurs first.

Subjects who discontinue treatment for unacceptable adverse event(s) will be followed until resolution or stabilization of the adverse event (i.e. the grade is not changing). If a subject stops treatment due to unacceptable adverse event(s) but has not demonstrated disease progression, then the subject will be followed with imaging studies every 9 weeks until the time of progression radiographically according to RECIST v1.1 criteria.

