6.1.3 Safety Population

The Safety Population will include all subjects who have received one dose of leronlimab (PRO 140). This population will be used for the analysis of safety parameters or measurements.

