8.4 Analysis of Safety Data

All safety analyses will be conducted using the Safety population. All data collected will be summarized according to the variable type. No inferential statistics are planned.

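### The Safety Population requires a leronlimab dose, which does not match Section 7.10 (any study therapy) and sits badly with Section 5.2; a patient given only carboplatin would drop out of the safety summary tables

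*Protocol*

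**What the plan says.** **Who is in the safety analysis.** Protocol 8.6.1.3 states that the Safety Population "will include all subjects who have received one dose of leronlimab (PRO 140"). The protocol synopsis has the same rule, and SAP 6.1.3 repeats it: "The Safety Population will include all subjects who have received one dose of leronlimab (PRO 140"). SAP 8.4 ties everything to that set: "All safety analyses will be conducted using the Safety population". Protocol 8.7.3.2 also uses it for the safety endpoints.

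**Who is evaluable for toxicity.** Protocol 7.10 sets a different trigger: "Any subject who receives at least one dose of study therapy will be evaluable for toxicity endpoints". The term study therapy is not defined. Section 6, on study treatment, says "Eligible subjects will receive the combination leronlimab (PRO 140) and carboplatin", and Table 6-1 lists carboplatin in its study drug column.

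**What is given on the first day.** Section 4.3 has leronlimab on Days 1, 8 and 15 "in combination with carboplatin AUC 5 on Day 1 of each cycle (every 21 days"), so both drugs fall on Cycle 1 Day 1. No section states which is given first.

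**Missed leronlimab.** Under Section 5.2, a subject who misses leronlimab in Cycle 1 because of toxicity is not replaced and is taken to have had a dose-limiting toxicity (DLT).

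**The concern.** The safety of the combination is an objective in both phases, and carboplatin is a protocol-specified component with its own toxicity table (Table 6-4). A population defined by leronlimab alone does not cover everyone exposed to study treatment. Someone who receives carboplatin, reacts, and never starts leronlimab has been treated on study and is evaluable under 7.10, but has no place in the tables that SAP 8.4 prescribes.

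By that route, omission would be triggered by the toxicity itself, which is the kind of exclusion a safety set should avoid. In Phase Ib there is a further mismatch. Section 5.2 would count such a patient as a DLT, while both the Safety Population and the Intent-to-Treat (ITT) population, which also needs a leronlimab dose, would leave her out. Protocol 8.7.3.1 places the primary analysis, including the maximum tolerated dose, on ITT.

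**Working it through.** The plan states no figure on this point, so there is nothing to reproduce. The check sets the rules side by side and then gives a sense of scale.

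**1. How each rule treats a patient given carboplatin and never leronlimab**

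| Source | Trigger | Patient counted? |
|---|---|---|
| Protocol 7.10 | At least one dose of study therapy | Yes, if study therapy includes carboplatin, as Section 6 and Table 6-1 suggest |
| Protocol 5.2 (Phase Ib) | Leronlimab missed for toxicity in Cycle 1 | Yes, as a DLT |
| Synopsis, Protocol 8.6.1.3, SAP 6.1.3 | A leronlimab dose | No |
| Protocol 8.6.1.1, SAP 6.1.1 (ITT) | A leronlimab dose and measurable disease | No |
| SAP 8.4.1, listings | All adverse events in the eCRF | Yes |

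**2. When such a patient can exist.** Two conditions must both hold: carboplatin is given before the first leronlimab injection, and leronlimab is not given at any later time. The documents establish neither. The Cycle 1 Day 1 list in Section 4.3.1 puts the entry "Carboplatin Administration (see" directly after leronlimab administration, and the schedule tables in both documents keep that row order. A list of visit procedures is not a stated sequence, so the case is possible but not shown. If leronlimab is given first, the number omitted by this route is 0.

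**3. How often, given both conditions.** The documents give no rate; Section 6.2.10 only places hypersensitivity among the rarer carboplatin reactions. Assume that a proportion p of patients stop at the first infusion and never receive leronlimab, with p from 0.1% to 2%. Planned numbers are up to 18 in Phase Ib and 30 in Phase II, so at most 18 + 30 = 48. Expected number = n × p; chance of at least one = 1 − (1 − p)^n.

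| Assumed p | Expected, n = 30 | At least one, n = 30 | Expected, n = 48 | At least one, n = 48 |
|---|---|---|---|---|
| 0.1% | 0.03 | 3.0% | 0.05 | 4.7% |
| 0.5% | 0.15 | 14.0% | 0.24 | 21.4% |
| 1% | 0.30 | 26.0% | 0.48 | 38.3% |
| 2% | 0.60 | 45.5% | 0.96 | 62.1% |

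These are conditional on carboplatin being given first throughout. They are not estimates for this trial.

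**4. What one omitted patient does to a table.** Protocol 8.7.3.2 summarises adverse events by phase and treatment group, so those are the relevant denominators.

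- Phase II, an event only she had: 1/30 = 3.3% with her, 0/29 = 0% without.
- Six-patient Phase Ib cohort, same situation: 1/6 = 16.7% with her, 0/5 without.
- Same cohort with one further DLT in another patient: 2/6 = 33.3% under Section 5.2, which meets the protocol's threshold of at least 33%; 1/5 = 20% if the population rule is applied.
- Phase II, an event that 10 others had and she did not (illustrative count): 10/30 = 33.3% with her, 10/29 = 34.5% without.

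The last line shows that omission lowers the rates of events she had and slightly raises the rates of those she did not have.

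**The case against.** The best defence is that the gap may never open. The visit list and both schedule tables name leronlimab first. The Safety Population needs a leronlimab dose at any time, not on Day 1. Table 6-4 holds and then resumes carboplatin for hypersensitivity up to Grade 3 and stops it permanently only at Grade 4. Its note adds: "Patients who discontinue carboplatin for any reason will be allowed to continue to receive leronlimab (PRO 140"). These points narrow the affected group sharply, and they stand. They do not close it: list order is not a stated sequence, and the note leaves the decision to the investigator, requires re-consent, and speaks of continuing leronlimab rather than starting it.

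Second, the events would not be lost. SAP 8.4.1 lists every adverse event in the eCRF by subject, serious events are reported under Section 9.4, the DSMB reviews them, and Section 5.2 would carry a Phase Ib case into the escalation decision. This also stands, and it confines the problem to summary tables and denominators.

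Third, Section 7.10 concerns assessment and evaluability and does not create an analysis set; both documents assign safety analyses to one population. That is fair. The conflict is between an evaluability rule and the analysis set meant to serve it, not between two declared analysis sets.

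Fourth, defining exposure by the investigational product is a recognised choice, and Section 6.2.9 describes carboplatin as standard of care. The choice is weaker here because the stated safety objective is the combination.

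**Conclusion.** The mismatch is real and rests on the text alone: the leronlimab-only Safety Population does not agree with Section 7.10 and sits badly with Section 5.2. Its consequence is conditional and small. A carboplatin-only patient would be missing from the safety summary tables but present in the listings. The effect is nil if leronlimab is given first or is given at any later time, and any rate is an assumption because the documents supply none.

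Two stronger readings are tempting and not supported. A reader might infer that any patient stopped by a reaction to the first carboplatin infusion is left out of every safety table; that needs both conditions in step 2 of the working, and neither is established. A reader might also infer that the rule can only understate toxicity. It understates the events the omitted patient had, but slightly raises the rates of all others, and a patient could go without leronlimab for reasons other than toxicity, such as withdrawal.

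This is a low-cost improvement to an analysis-set definition, not a threat to the trial's conclusions.

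**What to change.** In the protocol synopsis, Protocol 8.6.1.3 and SAP 6.1.3, define the Safety Population as all subjects who received at least one full or partial dose of leronlimab or carboplatin on study. That matches Section 7.10. All three places need the edit, or a contradictory copy will remain.

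Reconcile the new wording with Section 5.2, stating which set supports the Phase Ib DLT summary, so that a patient counted as a DLT during escalation is also in the table that reports it.

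The cost is one sentence in each of three places plus the reconciling statement. No new data are needed: Section 9.2 already collects adverse events from the first treatment. The change can be made before database lock. It concerns only who is analysed and takes no position on the order of administration or on clinical management.
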